### **Double-Blind Trial**

Individuals will be assessed in-person at baseline and weekly for 6 weeks of treatment with compounds administered as sublingual solutions in a double-blind, randomized procedure: subjects will receive either the CW solution or matched placebo. At the weekly visits throughout the treatment period, individuals will complete clinical scales and have a check-in with study staff.

In addition to clinical ratings and a check-in with study staff, neuropsychological testing will be performed at baseline and week 6 in order to assess cognitive performance. Finally, a subset of individuals will receive an hour-long MRI scan at baseline and week 6, with both resting state and task-related functional magnetic resonance imaging (fMRI) in each MRI session. In addition, a brief diffusion tensor imaging (DTI) sequence will also be acquired to examine white matter fiber tract integrity, and magnetic resonance spectroscopy (MRS) will be conducted to examine levels of certain metabolites in the brain. Subjects will also provide a buccal swab sample for genetic analysis at the baseline visit.

[figure not shown]
At the end of the baseline visit, eligible subjects will be randomized to either CW solution or placebo using a standard alternating procedure in accordance with the McLean Pharmacy. Subjects will be instructed on how to administer the compound, as described above.

For both the open-label and double-blind trials, the baseline and the final study visits are estimated to take approximately 3-4 hours, with the weekly visits in the interim estimated to take approximately 1 hour, and 15 minutes for phone check-ins, for a total of approximately 10-12 hours required to complete all possible visits. Urine samples will be collected at every other visit (Visits 1, 3, 5, and 7) to measure THC via GCMS (Quest Diagnostics) and to monitor for the presence of other substances throughout the study. Female subjects will be informed that their sample will also be used to confirm negative pregnancy (HCG) status; if at any point their urine tests positive for HCG, they will be excluded from the study. We are currently in communication with several groups that may be able to assess for CBD in urine; we hope to utilize one of these groups to quantify CBD in urine throughout the study.

Subjects will be given the option to complete daily study drug diaries manually (pencil and paper) or electronically. Adverse events and side effects will be assessed at weekly study visits and phone check-ins and all subjects will be advised to call study staff if they experience any adverse events.

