## RESEARCH DESIGN AND METHODS

Briefly describe study design and anticipated enrollment, i.e., number of subjects to be enrolled by researchers study-wide and by Partners researchers. Provide a brief summary of the eligibility criteria (for example, age range, gender, medical condition). Include any local site restrictions, for example, "Enrollment at Partners will be limited to adults although the sponsor's protocol is open to both children and adults."

This study is an investigation of 40 subjects who have expressed interest in using CBD for anxiety. Subjects will complete study visits at McLean Hospital. Following a preliminary phone screen and prior to any evaluation, all study subjects will be required to sign a McLean Hospital approved informed consent form that describes all study procedures. The phone screen includes questions related to medical history, substance use history, demographics, and screening questions from the OASIS (see below) to determine whether the subject has anxiety.

Individuals will be assessed at baseline and throughout 6 weeks of treatment with compounds administered as sublingual tinctures in a double-blind, randomized procedure: subjects will receive either a high CBD product or matched placebo. Each product will be analyzed and verified at an

outside lab for safety and potency. Subjects will self-administer 0.5 ml (15mg/ml) of CBD or placebo sublingually two times daily. At each weekly visit, individuals will complete clinical scales and have a check-in with study staff. Neuropsychological testing will be performed at baseline and the final visit in order to assess cognitive performance. Buccal swabs will be collected for DNA analysis from all participants in the double-blind phase. Finally, a subset of individuals will receive an hour-long MRI scan at baseline and the final visit, with both resting state and task-related functional magnetic resonance imaging (fMRI) in each MRI session. In addition, a brief diffusion tensor imaging (DTI) sequence will also be acquired to examine white matter fiber tract integrity, and magnetic resonance spectroscopy (MRS) will be conducted to examine levels of certain metabolites in the brain. Subjects will complete study drug diaries manually (pencil and paper) or electronically.

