In order to assess the efficacy of the dose chosen for the double-blind study, we will also conduct a small open-label trial of the CBD solution prior to initiating the double-blind study. This open-label trial will enroll up to 12 participants who are interested in using CBD, and who have anxiety. This trial will determine whether patients derive clinical benefits at the current dosage proposed for the active treatment arm of the double-blind trial. This trial will examine all components of the originally proposed study.

Subjects will be recruited through IRB-approved advertisements and flyers in regions that have approved medical marijuana. Additionally, medical marijuana healthcare facilities throughout New England, including CannaCare, Integr8, MMJ Physician Practice, and others, may also refer interested patients to contact the study recruitment line for further screening. These healthcare groups provide their interested patients who meet for general inclusion criteria with study recruitment materials. The total sample size for the double-blind study is 40 (20 CBD, and 20 placebo); up to 15 of each group (30 total) will also complete the MRI scanning protocol. For the open-label trial, the total sample size is 12.

Inclusion Criteria:

- 1) Subject has provided informed consent
- 2) Subject is 18 or older
- 3) Subject is a native English speaker or acquired English prior to age 5
- 4) Subject scores a minimum of 16 on the Beck Anxiety Inventory (BAI) OR a minimum of 8 on the Overall Anxiety Severity and Impairment Scale (OASIS) at the screening visit

Exclusion Criteria:

Subjects will be excluded if they report any of the following:

- 1) Non-native English speakers
- 2) Estimated IQ < 75
- 3) Meets criteria for DSM-IV classification of current substance abuse/dependence, psychotic disorder, bipolar disorder, or an eating disorder
- 4) A first-degree relative with a psychotic disorder
- 5) A history of head injury or loss of consciousness greater than 5 minutes
- 6) Currently uses marijuana or cannabinoid-based products more frequently than 1x/month
- 7) Female subjects will be excluded if they have a positive urine pregnancy test, or if they are currently breastfeeding
- 8) Presence of a serious medical illness, including liver, kidney, or cardiovascular disease, or neurological disorder
- 9) Allergy to coconut oil

- 10) Current use of valproate
- 11) Currently enrolled in other research studies or clinical trials involving interventions

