Additional Exclusions for MR Component:

- 1) Claustrophobia or metal implanted within the body, body piercings which are not removable
- 2) Cardiac pacemakers, metal clips on blood vessels (also called stents), artificial heart valve, artificial arms, hands, legs, etc., brain stimulator devices, implanted drug pumps, ear implants, eye implants or known metal fragments in eyes,
- 3) Exposure to shrapnel or metal filings (wounded in military combat, sheet metal workers, welders, and others), other metallic surgical hardware in vital area, certain tattoos with metallic ink, certain transdermal (skin) patches such as NicoDerm (nicotine for tobacco dependence), Transderm Scop (scopolamine for motion sickness), or Ortho Evra (birth control), certain intrauterine devices (IUDs) containing metal
- 4) Poor vision, as subjects must have normal or corrected-to normal vision for viewing of cognitive challenge paradigms during fMRI protocols

Concomitant medications will be allowed and will be assessed on a case-by-case basis with the study physician; participants may be excluded if they are taking strong inhibitors or inducers of CYP3A4 (e.g. fluconazole, fluoxetine, fluvoxamine, ticlopidine, St. John's Wort, etc.), CYP2C19 (e.g. ketoconazole, erythromycin, etc.), or CYP2D6 (e.g. paroxetine, bupropion, quinidine, ritonavir, glutethimide, etc.). Dosing schedules may be adjusted in order to offset CBD administration with concomitant medications to decrease the likelihood of any drug-drug interactions. Subjects must have been on stable medication/psychotherapy regimens for at least 3 months prior to starting the study.

Subjects who participate in the open-label phase of the study will not be eligible to also enroll in the double-blind study.

Briefly describe study procedures. Include any local site restrictions, for example, "Subjects enrolled at Partners will not participate in the pharmacokinetic portion of the study." Describe study endpoints.

This study is designed to assess individuals who have expressed interest in using CBD for anxiety. Subjects will complete study visits at McLean Hospital.

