A total of 52 (12 in the open-label phase, and 40 in the double-blind phase) female and male participants with anxiety, of minimum age 18, will complete a baseline visit including clinical ratings, an assessment of conventional medication use, quality of life measures, a neuropsychological test battery, a buccal swab sample, and optional neuroimaging (in a subset of participants who are eligible). Participants will subsequently be treated for 6 weeks with the CW sublingual solution. All participants will self-administer 0.5 ml (15 mg of CBD) of solution twice daily (BID). Participants will return to the laboratory or complete remote visits each week to complete clinical ratings and check in with study staff. After 6 weeks of treatment, participants will complete final clinical scales and quality of life measures, a complementary neuropsychological battery, and a corresponding neuroimaging component (where applicable). The open-label phase of the study is expected to take approximately 12 months to complete, and will assess the efficacy of the dose chosen for the double-blind study.

40 female and male participants will be enrolled in the double-blind phase. Study procedures will remain the same as the open-label phase, however participants will receive CW solution or placebo solution in a double-blind, randomized fashion. All participants will self-administer 0.5ml of solution BID for 6 weeks. The double-blind phase of the study is expected to take 24 months to complete.

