## RECRUITMENT PROCEDURES

Explain in detail the specific methodology that will be used to recruit subjects. Specifically address how, when, where and by whom subjects will be identified and approached about participation. Include any specific recruitment methods used to enhance recruitment of women and minorities.

Recruiting and enrollment will be the responsibility of the McLean study coordinators. Subjects will be recruited from a number of sources, including IRB-approved flyers and post cards, as well as online postings (including Rally) and via RPDR messaging. Medical marijuana certification facilities and anxiety clinics may also refer interested patients to contact the study recruitment line for further screening. Potential subjects for this study must be capable of understanding the nature of this study as well as the discomforts and potential benefits. All subjects will be given as much time as they want to consider their participation in the study and ask any questions they may have before being asked to sign the consent form.

Provide details of remuneration, when applicable. Even when subjects may derive medical benefit from participation, it is often the case that extra hospital visits, meals at the hospital, parking fees or other inconveniences will result in additional out-of-pocket expenses related to study participation. Investigators may wish to consider providing reimbursement for such expenses when funding is available

A tiered payment system will be used for a payment of \$75 at visit 1, \$30 each at visits 2, 3, 4, 5, and 6, and \$75 at visit 7 for a total of \$300; if termination occurs during any point of the visit, subjects are compensated at a rate of \$25 per hour. Subjects who participate in the scanning component of study will receive an additional \$75 at visit 1 and visit 7 for a total of \$450. Subjects will receive a completion bonus of \$50 if they complete the study, for a total of \$350 or \$500, depending on whether they receive MR scanning. Subjects may withdraw from the study at any point; and will still receive payment for the portion of the study they completed at a rate of \$25/hr.

For guidance, refer to the following Partners policies:

Recruitment of Research Subjects

<https://partnershealthcare-public.sharepoint.com/ClinicalResearch/Recruitment%20Of%20Research%20Subjects.pdf>

Guidelines for Advertisements for Recruiting Subjects

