#### **STATISTICAL APPROACHES**

All statistical analyses will be conducted using IBM SPSS Statistics (version 28). Data will be screened for outliers and any data points more than 2 standard deviations from the group means will be excluded. Additionally, data will be screened for skew, kurtosis, non-normality, and homogeneity of variance. If the assumptions of parametric inferential analyses are not met, the appropriate non-parametric analyses (e.g. Wilcoxon-Signed Rank Test) will be performed. Descriptive statistics will be used to characterize the demographic data. Baseline clinical and neuropsychological data will be assessed using 2-tailed paired *t*-tests to compare follow-up timepoints to baseline values. When needed, Bonferroni corrections for multiple comparisons will be utilized.

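### Allocation is described as alternating, which read literally contradicts the randomised label; no random sequence or concealment is described

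*Combined protocol and SAP*

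**What the plan says.** The second phase is called randomised in three places. Research Design and Methods describes compounds "administered as sublingual tinctures in a double-blind, randomized procedure" and later says "participants will receive CW solution or placebo solution in a double-blind, randomized fashion". The Double-Blind Trial section repeats the label: "administered as sublingual solutions in a double-blind, randomized procedure".

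The method is given once, in the Double-Blind Trial section. At the end of the baseline visit, eligible subjects are to be "randomized to either CW solution or placebo using a standard alternating procedure in accordance with the McLean Pharmacy". The alternating procedure is not defined.

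The planned size and split are in Research Design and Methods: "The total sample size for the double-blind study is 40 (20 CBD, and 20 placebo".

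Statistical Approaches and Monitoring and Quality Assurance say nothing about sequence generation, blocking, stratification, custody of a list or concealment. The front matter and a figure just before the allocation sentence are not reproduced in the text under review, so absence can be asserted only for the text that is visible.

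**The concern.** Assigning participants in strict turn is systematic. Whoever knows the order of enrolment and a single assignment knows all of them. A trial run that way is quasi-randomised, whatever it is called.

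What is at stake is selection at entry. Allocation follows eligibility decisions that leave room for judgement: "Concomitant medications will be allowed and will be assessed on a case-by-case basis with the study physician". Separately, "Recruiting and enrollment will be the responsibility of the McLean study coordinators". If anyone with influence over entry can foresee the next arm, the two groups of 20 can differ before treatment starts, and the analysis cannot restore the lost comparability.

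There is a conceivable route to a guess. Background and Significance gives the product about 0.8 mg/ml THC, and the Double-Blind Trial section schedules urine THC tests at Visits 1, 3, 5 and 7. The documents do not say who sees those results or whether this amount is detectable, so this is a possibility and not a demonstrated leak.

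**Working it through.** **Inputs from the protocol.** N = 40, split 20 and 20 (Research Design and Methods); allocation by an alternating procedure (Double-Blind Trial). The split reproduces: 20 + 20 = 40. Alternation gives exactly 20/20 at N = 40, as would many random lists, so the planned split does not show which is meant.

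**Predictability.** The number of possible sequences, and the expected share of correct guesses by someone who knows all past assignments:

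| Scheme | Possible sequences | Correct guesses |
|---|---|---|
| Strict alternation, random start | 2 | (39 + 0.5)/40 = 98.75% |
| Permuted blocks of 4 | 6^10 = 60,466,176 | about 71% (simulated) |
| One random 20/20 list | C(40,20) = 137,846,528,820 | about 59% (simulated) |
| Simple randomisation | not restricted | 50% |

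**Effect on a between-arm test (illustration).** None of the following assumptions is in the documents:

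- Once the next arm is known, enrolment shifts the expected outcome by η = 0.1, 0.2 or 0.3 SD in the direction that favours CBD: up by η for entrants bound for one arm, down by η for the other.
- The drug has no effect.
- The arms are compared by a two-sided 5% two-sample t test with 20 per arm.

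If all 40 next arms are known, the expected difference is 2η. The noncentrality is 2η / √(2/20) = 2η / 0.3162, with 38 degrees of freedom:

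- η = 0.1: 0.632, rejection rate 9.5%
- η = 0.2: 1.265, rejection rate 23.4%
- η = 0.3: 1.897, rejection rate 45.6%

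If the arm is known only after the first k participants, the expected difference is 2η × (40 − k)/40. For k = 20 this is η. Simulated rates (200,000 trials per cell; the all-40 row is the noncentral t result above):

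| Next arm known for | η = 0.1 | η = 0.2 | η = 0.3 |
|---|---|---|---|
| nobody | 5% | 5% | 5% |
| last 10 | 5.3% | 6.1% | 7.2% |
| last 20 | 6.0% | 9.3% | 14.8% |
| last 30 | 7.3% | 15.0% | 27.7% |
| all 40 | 9.5% | 23.4% | 45.6% |

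**Comparator: permuted blocks of 4 and 6.** Suppose every past assignment leaks and the enroller steers toward whichever arm has fewer so far, with no steering when they are tied (40,000 simulations per value of η). Used for the last 20 participants, the rates are 5.1%, 5.4% and 6.3%. Used for all 40, they are about 5.5%, 7.4% and 10%. The like-for-like comparisons at η = 0.3 are therefore 14.8% against 6.3% (last 20) and 45.6% against about 10% (all 40).

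**The case against.** The strongest reply is that the wording may be loose. The sentence itself uses the verb for random assignment, three statements carry the same label, and the pharmacy is named. A pharmacy-held random list may lie behind it, in which case nothing is wrong with the design. That reading is open, and the documents neither confirm nor exclude it.

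Second, no leak is shown. The trial is described as double-blind with matched placebo, and nobody who enrols is said to learn assignments. The medication review belongs to the study physician and enrolment to the coordinators, so the discretion is not shown to sit with one person. This stands, and it is why the table begins with a row showing no inflation. But masking and a named custodian are not a random sequence, and neither states how the next assignment is concealed.

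Third, the error rates concern a test the plan does not name. Statistical Approaches specifies paired tests "to compare follow-up timepoints to baseline values", and those do not rest on random assignment. This also stands; the rates are illustrative, and the top of the range needs every next arm known from the first participant. The contradiction does not depend on them. Any causal reading of a difference between the CBD and placebo groups does depend on how those groups were formed.

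**Conclusion.** The concern holds and the sentence must be fixed. What is established is a contradiction in the text: the only stated allocation rule, followed as written, is not random, and no sequence generation or concealment is described. What is not established is how the pharmacy allocates in practice. If a random list is already in use, this is a wording error. If alternation is literal, it is a design flaw, and the second phase is quasi-randomised.

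The firm measure of size is 2 possible sequences, with one known assignment fixing the other 39. The false-positive rates run from 5% (no inflation) to 45.6% across the assumed scenarios and rest entirely on the assumed shift, the assumed extent of foreknowledge and an assumed between-arm t test.

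**What to change.** 1. Ask the pharmacy which method is used.
2. If a random list is already in place, correct the allocation sentence in the Double-Blind Trial section to say so, and state who holds the list and how the next assignment is concealed.
3. If not, replace the alternating procedure. Example wording: *Eligible subjects will be assigned 1:1 to CW solution or placebo by the next entry of a computer-generated list in permuted blocks of randomly varying, undisclosed size. The pharmacy generates and holds the list and conceals it from those who screen, enrol or rate subjects.* Other concealed random lists would serve equally well.
4. If participants have already been allocated by alternation, report the allocation as quasi-randomised.

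The cost is one or two sentences and a short list-generation script. The pharmacy is already involved, and sample size and visits do not change. With freely varying blocks of 4 and 6, an incomplete last block gives a 21:19 split in about 23% of lists and never a larger imbalance. If exactly 20/20 is wanted, fix the block sizes to total 40 and shuffle their order (for example 4 × 4 + 4 × 6 = 40), or use a single random 20/20 list.

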#### Clinical Ratings

The Structured Clinical Interview for DSM-V Patient Version (SCID-P) and the SCID-P Substance Abuse/Dependence Module or the Quick Structured Clinical Interview for DSM-V Disorders (QuickSCID) will be administered to all study participants during visit 1 by the Principal Investigator, a Clinical Neuropsychologist or trained Clinical Research Assistant. Subjects will also complete clinical rating scales and questionnaires that have been shown to provide reliable estimates of current clinical state and are easily administered. They will also complete quality of life measures. All subjects will be given the following measures at the baseline and final visits that take approximately one hour to complete:

Subjects will also complete a subset of these measures, specifically the anxiety and mood-related measures [REDACTED], along with the SEQ, at each weekly visit. An Abuse Liability Rating Scale (ALR) will be completed at V3 and V7.

Please note that if suicidality is endorsed spontaneously, on any of the clinical scales, or during the SCID or weekly check-ins with study staff, the patient will be immediately assessed for suicidality risk. Please see “Suicidality SOP” attachment for further information.

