### **CBD Administration**

CBD has been shown to have an extremely low side effect profile and since the total amount of THC will not exceed 0.3% by weight, we do not expect significant side effects or psychoactive effects. CBD is not a scheduled substance, and there is no risk of intoxication or addiction to CBD. As with any clinical trial, there are risks of experiencing side effects from the administration of CBD or placebo; these side effects are very rare. Cunha et al. (1980) reported no signs of toxicity or serious side effects; in this two-part, placebo-controlled, double blind study, healthy volunteers were given 3 mg/kg of CBD or placebo per day for 30 days, and patients with epilepsy were given 200-300mg CBD or placebo per day for 4.5 months. The total dose of CBD per day for the current study will be 30mg – thus, we expect no significant side effects. Other studies have reported no adverse effects of CBD in patients with Huntington’s disease, schizophrenia, and Parkinson’s disease after repeated administration (Consroe et al. 1991; Leweke et al. 2012; Zuardi et al. 2006 and 2009). Subjects will have the opportunity to report adverse effects at their weekly check-in visits via direct contact with the PI and study staff. This weekly reporting will reduce the likelihood that subjects experience significant negative side effects for any significant period of time, and the PI as well as they study physician will be reachable by page 24 hours a day 7 days a week.

Sublingual solutions are unlikely to be viewed by the public as analogous to recreational smoked marijuana, thus decreasing the risk of the subject experiencing any potential negative appraisal arising from perceived notions associated with marijuana use while partaking in this study.

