NOTE: In addition to the adverse event reporting requirements of the sponsor, the principal investigator must follow the Partners Human Research Committee guidelines for Adverse Event Reporting

In the unlikely event that an adverse event occurs, it will be reported by the primary investigator to the Institutional Review Board, and the IRB's guidelines will be followed to ensure adequate reporting and response. All adverse events will be reported to the Partners Healthcare Internal Review Board for their records.

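### The 2-SD exclusion has no exemption for safety scales, and the one stated comparison cannot cover the abuse-liability scale (ALR), which is rated only on treatment

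*Combined protocol and SAP*

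**What the plan says.** Clinical Ratings schedules the scale at two visits: "An Abuse Liability Rating Scale (ALR) will be completed at V3 and V7". Visit 1 is baseline and visit 7 is the final visit, so both ratings are made on treatment and there is no pre-treatment value.

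Statistical Approaches is the only statistical section, and no text in it is blacked out. Three parts of it matter here:

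- The outlier screen: "any data points more than 2 standard deviations from the group means will be excluded". No variable is exempted.
- The stated comparison: "Baseline clinical and neuropsychological data will be assessed using 2-tailed paired" t-tests, used to "compare follow-up timepoints to baseline values".
- A non-parametric fallback whose only example, the Wilcoxon signed-rank test, is also paired.

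The section does not mention the ALR, adverse events or safety.

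The Double-Blind Trial section sets up a randomised comparison in which "subjects will receive either the CW solution or matched placebo". Research Design and Methods gives 20 participants per arm. On adverse events, the protocol says that "Adverse events and side effects will be assessed at weekly study visits and phone check-ins" and, under Data and Safety Monitoring, that "All adverse events will be reported to the Partners Healthcare Internal Review Board for their records".

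**The concern.** There are two linked gaps.

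First, the ALR has no planned analysis. A change-from-baseline test needs a baseline, and the ALR has none. The natural contrast, CBD against placebo at each visit, is not named. It is not named for any other outcome either, so this is the safety part of a plan-wide omission.

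Second, the outlier screen suits a safety scale badly. On such a scale the few high scores are the information sought, not noise. The protocol itself expects few psychoactive effects (CBD Administration), so scores bunched at the floor are plausible. In that setting a 2-SD rule removes high scores and leaves the floor untouched. The non-parametric fallback is no protection: it comes after the exclusion, and nothing says that excluded points are restored.

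At stake is whether the placebo-controlled phase can say anything reliable about abuse liability. The ALR is the only measure of it named in the public text. The product supplies some THC as well as CBD: 0.5 ml × 2 per day × 0.8 mg/ml = 0.8 mg per day.

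**Working it through.** The plan gives no figure to reproduce, so the check applies the 2-SD rule directly.

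**Inputs from the protocol.** 20 per arm; ALR at V3 and V7 only; exclusion beyond 2 SD of the group mean.

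**Assumptions.** The group is the randomised arm; the screen is applied once with the sample SD; participants with nothing to report sit at a common floor, set to 0. The documents give neither the floor nor the range.

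**Equal scores.** If k of n participants share one score above the floor, that score lies

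z = √[(n − k)(n − 1) / (k n)]

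sample SDs above the mean. With n = 20:

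| k | z | Deleted? |
|---|---|---|
| 1 | √(19 × 19 / 20) = 4.25 | yes |
| 2 | √(18 × 19 / 40) = 2.92 | yes |
| 3 | √(17 × 19 / 60) = 2.32 | yes |
| 4 | √(16 × 19 / 80) = 1.95 | no |

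**Unequal scores.** Rescale so that the highest score is 1, and let T be the sum of all scores, so T ≤ k. Each score lies between 0 and 1, so its square is no larger than itself, and the sum of squares about the mean is at most T − T²/n = T(n − T)/n. The top score is (n − T)/n above the mean. Hence

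z² ≥ (n − T)(n − 1) / (nT) ≥ (n − k)(n − 1) / (nk).

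Equal scores are therefore the mildest case. With one to three participants above the floor, the highest score is deleted whatever the scores are.

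**Example.** Scores 1, 1, 5 and seventeen zeros: mean 7/20 = 0.35, SD 1.137. The 5 lies (5 − 0.35)/1.137 = 4.09 SD out and is deleted; the 1s, at 0.57 SD, stay. The arm mean falls to 2/19 = 0.11.

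**If the group means all 40 participants.** The same formula with n = 40 gives 2.14 for seven equal scores (deleted) and 1.98 for eight (kept).

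**Other score shapes.** Simulated share of arms of 20 in which the maximum is deleted:

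| Assumed distribution | Maximum deleted |
|---|---|
| Normal | about 35% |
| Exponential | about 90% |
| Flat, 0 to 10 | about 5% |

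The effect depends heavily on shape. It is severe for sparse or skewed scores and minor for flat ones.

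**Precision of a by-arm comparison.** An event seen in 0 of 20 has an exact 95% upper limit of 1 − 0.025^(1/20) = 16.8%. Fisher's two-sided test against 0/20 gives p = 0.106 for 4/20 and p = 0.047 for 5/20. A between-arm ALR result can only be descriptive.

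**The case against.** The strongest reply is that the two halves of the point pull apart: the section is said to leave the ALR out, yet its outlier rule is said to reach it. The rule opens a run of checks that lead into the stated tests, so it may be meant only for data entering those tests. That reading is fair, and deletion of ALR scores is therefore possible rather than established. But the rule's wording covers any data point, and it would also apply once a between-arm ALR test is added, so the exemption still needs to be written.

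A second reply is that the scale's range and floor are unknown. This stands, and it is why the result is conditional and the flat case is shown.

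Three stronger readings are tempting, and the documents do not support them:

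- *The plan prescribes an impossible test for the ALR.* It does not; it is silent on the scale.
- *Adverse events will go unreported or participants unprotected.* Events are collected weekly, can end participation and all go to the IRB. Silence does not bar a table by arm, and an SD screen does not naturally apply to event counts.
- *The screen would hide evidence against the statement that "there is no risk of intoxication or addiction to CBD".* That sentence is a pre-study risk statement about CBD, not a trial hypothesis, and no specific aim concerns abuse liability. The same section also limits THC to 0.3% by weight, and urine is tested for THC at visits 1, 3, 5 and 7.

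Finally, the missing between-arm comparison is not peculiar to safety. That is correct, and it limits how far this point should stand alone.

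**Conclusion.** The point holds in a limited form. The exclusion rule has no exemption for safety scales, and the stated paired comparison cannot be used for a scale without a baseline. Both follow from the text.

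Harm to the ALR is conditional on two things: that the screen is applied to it, and that most participants score at the floor. Given both, losing the top score is certain with one to three participants above the floor in an arm of 20. Complete loss is narrower: with equal scores it stops at four. Without the floor assumption, the chance of losing the maximum runs from about 5% to about 90% across the shapes tried.

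The change is worth making because it corrects a stated rule at almost no cost. The absence of an adverse-event table by arm is a secondary matter of detail.

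**What to change.** Add to Statistical Approaches, for the double-blind phase:

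> Safety measures, including the ALR, are exempt from the 2-SD exclusion. ALR scores at V3 and at V7 will be compared between CBD and placebo with a non-parametric between-group method and a 95% confidence interval, as descriptive estimates.

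A sensible accompanying line would tabulate adverse events by randomised arm. All of this should sit as the safety sub-section of a general CBD-versus-placebo analysis, not as a stand-alone addition.

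The cost is a short paragraph of wording and about two tables. No new visits, data or ALR baseline are needed. The downside is wide intervals at 20 per arm, which is why the estimates should be labelled descriptive.
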